4.2 Exclusion Criteria

Subjects are excluded from the study if any of the following exclusion criteria are met:

1. Unable or unwilling to meet requirements of the study.
2. Unable to communicate with suitable verbal/auditory and/or tactile sign language (in the opinion of the investigator)
3. Participation in a clinical study with an investigational drug in the past six months.
4. Pre-existing ocular conditions that would interfere with the interpretation of study endpoints (for example, glaucoma, corneal or significant lenticular opacities, moderate / severe cystoid macular oedema, macular hole) in both eyes.
5. Complicating systemic diseases in which the disease itself, or the treatment for the disease, can alter ocular function. Examples are malignancies whose treatment could affect central nervous system function (for example, radiation treatment of the orbit; leukemia with CNS/optic nerve involvement).
6. Subjects with diabetes or sickle cell disease would be excluded if they had any manifestation of advanced retinopathy (e.g. macular edema or proliferative changes).
7. Prior ocular surgery within three months.
8. Any other condition that would not allow the potential subject to complete follow-up examinations during the course of the study and, in the opinion of the investigator, makes the potential subject unsuitable for the study.

Subjects will not be excluded based on their gender, race or ethnicity.

4.3 Reproductive Potential

Pregnant or nursing patient will not be excluded. Subjects who become pregnant while on study may continue participation in the study. Pregnancy information, including outcome, as reported by the patient will be recorded. Pregnant and nursing subjects will undergo study assessments without instillation of ocular drops for the duration of their pregnancy and nursing. All study assessments which cannot be done without ocular drops will be omitted while the subject is pregnant and nursing.

4.4 Discontinuation of Subjects

A subject may withdraw from the study at any time for any reason without prejudice to their future medical care by the physician or at the institution. The investigator or sponsor may withdraw the subject at any time (eg, in the interest of subject safety).

Comments (spontaneous or elicited) or complaints made by the subject must be recorded in the source documents.

Subjects who withdraw or are discontinued from participation in the study may be replaced at the discretion of the sponsor.

4.4.1 Reasons for Discontinuation

The reason for withdrawal must be determined by the investigator and recorded in the subject's medical record. If a subject is withdrawn for more than 1 reason, each reason should be documented in the source document.

Reasons for discontinuation include but are not limited to:

- Protocol deviation
- Withdrawal by subject/parent/guardian
- Lost to follow-up
- Physician decision
- Unwilling or unable to comply with protocol
- Study terminated by sponsor
- Site terminated by sponsor
- Other (must be specified by investigator)

4.4.2 Subjects “Lost to Follow-up” Prior to Last Scheduled Visit

A minimum of 3 documented attempts must be made to contact any subject lost to follow-up at any time point before withdrawing him\ her from the study.

5 PRIOR AND CONCOMITANT TREATMENT

5.1 Prior Treatment

Prior treatment (medications/nutritional supplements/therapies/procedures) includes all treatment (pharmacologic and non-pharmacologic) received within 90 days prior to obtaining IC. Prior treatment information must be recorded.

5.2 Concomitant Treatment

Concomitant treatment (medications/nutritional supplements/therapies/procedures) refers to all treatment taken between the dates of obtaining IC and the final protocol-defined assessment. Concomitant treatment information must be recorded.

5.2.1 Permitted Treatment

Treatments not specifically listed in Section [5.2.2](#) are permitted.

5.2.2 Not recommended Treatment

The patient is asked to notify the investigator in case he\she takes any of the following not recommended medication in the course of the study:

:

- Plaquenil
- Thioridazine
- Clofazimine
- Deferoxamine
- Phenothiazine
- Chlorpromazine
- Cisplatin
- Valproic acid
- Any other drugs with known visual side effects

6 INVESTIGATIONAL PRODUCT

Not applicable. This is a natural history study, and no investigational product will be administered.

7 STUDY PROCEDURES

7.1 Study Schedule

See [Table 1](#) for study procedures.

The 1 year and 2 year follow-up visit assessments may be performed within a \pm 30-day window.

7.1.2 Baseline visit

The following procedures will be performed:

- Obtaining written IC (and assent if applicable) by subject, and/or the subject's parent(s) or legally authorized guardian(s)
- Assessment of eligibility according to the inclusion/exclusion criteria
- Collection of medical history, including subject's ocular history, previous medications, and previous test and examination
- NEI VFQ-25 plus its additional items
- Concurrent Medical Conditions
- Pregnancy or nursing status
- Concomitant treatment (medications/nutritional supplements/therapies/procedures)
- Refraction and BCVA
- Visual field assessments (kinetic and static)
- Clinical ophthalmic examination
- Microperimetry
- Fundus Photography
- Fundus autofluorescence
- Optical Coherence Tomography
- Confirmation of eligibility according to the inclusion/exclusion criteria
- Multifocal electroretinogram
- Full field electroretinogram

7.1.3 1 year and 2 year follow-up visit

The following procedures will be performed:

- NEI VFQ-25 plus its additional items
- Concurrent Medical Conditions \ Disease progression
- Pregnancy or nursing status
- Concomitant treatment (medications/nutritional supplements/therapies/procedures)
- Refraction and BCVA
- Visual field assessments (kinetic and static)

- Clinical ophthalmic examination
- Microperimetry
- Fundus Photography
- Fundus autofluorescence
- Optical Coherence Tomography
- Multifocal electroretinogram
- Full field electroretinogram

7.1.4 Additional Care of Subjects after the Study

No after care is planned for this study.

7.2 Study Evaluations and Procedures

7.2.1 Demographic and Other Baseline Characteristics

7.2.1.1 Demographics

Subject demographic information including sex, age, race, and ethnicity will be collected.

7.2.1.2 Medical history

Medical history, including subject's ocular history, previous medications, and previous test and examination will be collected at baseline.

On this visit, if the patient has been previously visited at the clinical centre, the available historical data on visual related assessments as described in section 7.2.2 will be collected and will form the retrospective data.

7.2.1.3 Concurrent Medical Conditions

Any clinically significant medical condition will be recorded.

Deafness severity or grade will also be recorded

7.2.2 Measures of Disease Progression

The study procedures described in this section must be performed by trained site personnel.

7.2.2.1 Refraction and Best Corrected Visual Acuity

Visual acuity with manifest refraction will be assessed in both eyes using a standardized ETDRS protocol. Following complete refraction of both eyes by a trained refractionist, BCVA measurements will be obtained for each eye. Subjects will be allowed as much time as necessary and will be encouraged to read each letter. If they are unsure about a letter, they will be asked to guess. Details are provided in the Technical Manual of Procedures.

7.2.2.2 Visual Field Assessments

Visual field measurements will be made in both eyes using the Octopus 900 (Haag-Streit International) with the semiautomatic kinetic perimetry module and a full field static perimetry protocol as defined in the Technical Manual of Procedures. Visual field measurements will be

evaluated by the Coordinating center.

7.2.2.3 Clinical ophthalmic examination

Clinical ophthalmic examination includes:

External Ocular Examination: to assess the motility of the extraocular muscles and the appearance and function of the eyelids before the instillation of any dilating or anesthetic eye drops;

Slit Lamp Examination (SLE) (biomicroscopy), to assess eyelids, lashes, conjunctiva, cornea, lens, iris and anterior chamber. SLE must be performed before the instillation of any dilating or anesthetic eye drops or the fluorescein agent.

Intraocular Pressure (IOP) measurement, performed using either Goldmann applanation tonometry or a handheld applanation tonometer (e.g. Tonopen) after instillation of a topical anesthetic.

Dilated Fundus Ophthalmoscopy, performed after dilation of the pupil, in order to assess the retina, macula, choroid and optic nerve head.

7.2.2.4 Micropertimetry

Microperimetry will be performed using the MP-1 or Maia to more accurately access the central visual field by tracking fundus movements while the patient looks steadily at the fixation target.

7.2.2.5 Fundus photography

Non-stereo images of macula and eight non-stereoscopic photographic fields surrounding the macula will be taken through a dilated pupil to document the appearance of the posterior pole.

7.2.2.6 Fundus autofluorescence

Infrared reflectance and FAF (blue) imaging covering 30° degree and centred on the macula will be obtained using the Spectralis (Heidelberg Engineering) or other sponsor-approved FAF machine. Details are provided in the Technical Manual of Procedures

7.2.2.7 Ocular Coherence Tomography

A volume scan capturing a 30 x 25 degree region of the posterior pole of the retina of both eyes will be obtained using the Spectralis (Heidelberg Engineering) or other sponsor-approved OCT machine. Details are provided in the Technical Manual of Procedures.

7.2.2.8 Multifocal electroretinogram

Multifocal electroretinograms will be performed in both eyes (monocular stimulation) using a Reticom (Roland Consultant) or Espion D15 (Diagnosis) equipment according to the International Society for Clinical Electrophysiology of Vision standards(Hood, Bach et al. 2012). Details are provided in the Technical Manual of Procedures.

7.2.2.9 Electroretinography

Full field electroretinograms will be performed in both eyes using a Reticom (Roland Consultant) or Espion D15 (Diagnosis) equipment according to the International Society for Clinical Electrophysiology of Vision standards(McCulloch, Marmor et al. 2015). Scotopic and photopic assessments will be performed as follows:

- Dark-adapted (40 minutes)
- Rod response (0.01 ERG)
- Maximal combined rod/cone response (3 ERG)
- Light-adapted (10 minutes)
- Cone response (3 ERG)
- Response to flicker (30 Hz flicker ERG)

Details are provided in the Technical Manual of Procedures.

If a patient has a non-detectable ERG response to all stimuli at previous visit (or as assessed by medical history), ERG assessments will not be performed at subsequent study visits.

7.3 Patient Reported Outcomes

Patient reported outcome assessments will not be administered to subjects less than 16 years old.

25-ITEM NATIONAL EYE INSTITUTE VISUAL FUNCTIONING QUESTIONNAIRE AND ITS ADDITIONAL ITEMS

Vision-related function and QOL will be assessed using the NEI VFQ-25 and its additional items, a valid and reliable questionnaire developed to measure the influence of visual impairment on QOL due to chronic eye diseases/conditions (Mangione, Lee et al. 2001). The questionnaire will be administered by an interviewer (interviewer-administered format) during the scheduled visits so that any interaction between subject and physician will not influence the subject's responses to the questionnaire. On average, it takes approximately 10 minutes to administer.

The NEI VFQ-25 includes 25 items plus 1 general health item and an appendix of 13 supplementary items (additional items) that are used to expand the scales. These additional items enhance the reliability of the specific scales and are likely to improve responsiveness of the sub-scale to changes over time. The NEI VFQ-25 and its additional items result in 11 vision-related constructs/scales (37 items) assessing global vision, difficulty with near vision activities, difficulty with distance vision activities, limitations in social functioning due to vision, role limitations due to vision, dependency on others due to vision, mental health symptoms due to vision, driving difficulties, limitations with peripheral vision, limitations with color vision, and ocular pain and a general health scale (2 items). There is limited information on the performance of the NEI VFQ-25 in subjects with Usher Syndrome; therefore the SF-12v2 and PGI-S (see below) will also be assessed to establish the psychometric properties (validity, reliability, and sensitivity) of the NEI VFQ-25 and its additional items in this patient population.

Questionnaire will be provided in the patient language and administrated with the help of a sign language interpreter, as required / recommended by national law or local procedures

8 DATA MANAGEMENT AND STATISTICAL METHODS

8.1 Data Collection and source data

The investigators' authorized site personnel must enter the information required by the protocol in the Clinical Record Form (CRF)

The investigator is responsible for maintaining adequate and accurate medical records from which accurate information is recorded onto CRFs, which have been designed to record all observations and other data pertinent to the clinical investigation. Case report forms must be completed by the investigator or designee as stated in the site delegation log.

All key data must be recorded in the subject's medical records.

Original source data will include, but are not limited to subject's medical file, including all visual assessments.

All data sent to the sponsor must be endorsed by the investigator.

A study monitor will verify the contents against the source data per the monitoring plan. If the data are unclear or contradictory, queries are sent for corrections or verification of data.

Essential documents must be maintained according to ICH GCP requirements .

8.2 Statistical Analysis Process

Continuous variables at each scheduled visit will be summarized using descriptive statistics (n, mean, quartiles, standard deviation, minimum and maximum). For categorical variables, tabular summaries will consist of presenting the number and percentage in each category, including missing category, if applicable. The annual rate of progression of each endpoint will be estimated by means of regression models for the analysis of longitudinal data, as appropriate.

The main analysis will be done on data collected prospectively, but a secondary analysis will be performed considering also the retrospective data recovered in patients medical history.

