Optical Coherence Tomography*	•	•	•
Multifocal electroretinogram ^f **	•	•	•
Full field electroretinogram ^g **	•	•	•

Notes:

- a It may take approximately 2 days to complete all required assessments.
- b Informed consent will be obtained
- c Includes family history, vision-related medical history, vision-related family history and abstracting of all previous available tests and examination.
- d The NEI VFQ-25 will be administered at the start of the scheduled visit so that any interaction between physician and subject will not influence the subject's responses to the questionnaires.
- e Clinical ophthalmic examination will include slit lamp examination, direct and/or indirect ophthalmoscopy, and cataract grading.
- f To be performed only in patients with stable fixation
- g If a patient has a non-detectable ERG response at previous visit, ERG assessments will not be performed at subsequent study visits.
- * to be performed without dilation in pregnant subjects
- ** to be not performed in pregnant subjects

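### Does the secondary analysis need a written rule for which historical values may be combined with the study values?

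*Combined protocol and SAP*

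**What the plan says.** Section 8.2 (Statistical Analysis Process) bases the main analysis on data collected prospectively. It then states that "a secondary analysis will be performed considering also the retrospective data recovered in patients medical history". The annual rate comes from longitudinal regression models that are not specified further.

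Section 7.2.1.2 (Medical history) defines the extra data. For patients already known to the centre, "the available historical data on visual related assessments as described in section 7.2.2 will be collected and will form the retrospective data". Table 1, note c, asks for all earlier available tests and sets no look-back limit.

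Three exclusion criteria in section 4.2 bear on whether a value can be interpreted:
- Criterion 4: "Pre-existing ocular conditions that would interfere with the interpretation of study endpoints (for example, glaucoma, corneal or significant lenticular opacities", with further examples, and only where both eyes are involved. The synopsis version has no both-eyes condition.
- Criterion 7: "Prior ocular surgery within three months".
- Criterion 3: "Participation in a clinical study with an investigational drug in the past six months".

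Table 1 and section 7.1.2 place the eligibility check at baseline; section 7.1.3 does not repeat it at years 1 and 2. For the study visits, section 7.2.2.1 says "Visual acuity with manifest refraction will be assessed in both eyes using a standardized ETDRS protocol", and section 7.2.2.2 has Octopus 900 fields "evaluated by the Coordinating center".

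**The concern.** The protocol itself regards certain eye conditions as spoiling its endpoints, yet it attaches that judgement to the baseline date only. Take a patient operated for opacities in both eyes four months before baseline. Criterion 7 no longer applies and the opacities are gone, so the patient is eligible, and the acuity from before the operation belongs to the retrospective data. The same opacities at baseline would have excluded the patient. Values recorded during a drug study that ended more than six months earlier could enter a natural-history rate in the same way. It is also not fully clear whether historical acuities and fields must have been obtained by the study methods.

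The stake is the combined annual rate. Section 2.1 expects slow progression and large measurement variability, so a modest bias could be a noticeable share of the decline. Historical visits also lengthen the time span and shrink the standard error, so a biased combined rate would look like the more precise one.

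**Working it through.** **No plan figure to reproduce.** Section 8.4 reports no formal sample size computation, and the documents give no SD, decline, share of patients with history or share affected. Every input below is an assumption except the number of patients (about 50) and the visits at 0, 1 and 2 years.

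**Assumptions.** Residual SD 1; random intercept with intraclass correlation 0.8; history in 30% or in all patients, on one of four schedules; a share f = 0.10 of patients with history affected; affected values d = 2 residual SD too low. Lower means worse, so a positive shift makes decline look slower.

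**Formula when all patients have the same visits.** With t̄ the mean visit time and S = Σ(t − t̄)², the slope shift is −f·d·Σ(t_h − t̄)/S, summed over the depressed historical visits, and the SE is 1/√(50·S). For history at −3, −2, −1: t̄ = −0.5 and S = 17.5.
- All three values depressed: deviations −2.5 − 1.5 − 0.5 = −4.5, so the shift is 0.2 × 4.5/17.5 = 0.051.
- Only the last depressed: 0.2 × 0.5/17.5 = 0.0057.
- SE = 1/√875 = 0.034. Prospective visits alone (S = 2) give 1/√100 = 0.100.

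| History (years) | t̄ | S | Shift, all depressed | Shift, last only | SE |
|---|---|---|---|---|---|
| −1 | 0.5 | 5 | 0.060 | 0.060 | 0.063 |
| −3, −2, −1 | −0.5 | 17.5 | 0.051 | 0.0057 | 0.034 |
| −5, −3, −1 | −1 | 34 | 0.035 | 0.000 | 0.024 |
| −10, −5, −2 | −2.33 | 101.3 | 0.020 | −0.0007 | 0.014 |

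**History in 30% of patients (generalised least squares).** All depressed, in the same order: 0.031, 0.041, 0.031, 0.019. Last only, for the three longer schedules: 0.0048, 0.0003, −0.0004.

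**Size of the all-depressed case.** Over both sets the shift is 0.019 to 0.060 per year, or 0.38 to 1.52 SE. At 20% affected it doubles to 0.038 to 0.120 (0.76 to 3.04 SE). With random slopes (SD 0.5) and 10% affected it is 0.012 to 0.060 (0.12 to 0.66 SE). Against an assumed decline of 0.2 per year, 0.012/0.2 = 6% to 0.060/0.2 = 30% would be hidden.

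**What drives it.** These figures need a deficit present at every historical visit, in the longest schedule back to ten years before baseline. If the condition arose recently, as the four-month example allows, only the last value is low and the shift nearly vanishes unless that is the sole historical visit. If the last two of three values are low, it is 0.005 to 0.023. The direction is not fixed either. What counts is position relative to the mean visit time, not to baseline: at −2 in the longest schedule the deviation is +0.33, and decline looks very slightly faster.

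**Cost of leaving values out.** At 10% affected, dropping them raises the SE by 1.6% to 5.2%. Keeping them gives the smaller mean squared error when d is below √(SE_out² − SE_in²) divided by the shift per unit of d. For −3, −2, −1 in all patients: √(0.03536² − 0.03381²) = 0.0104, and 0.0104/0.0257 = 0.40 residual SD. Over the grid this break-even runs from 0.40 to 0.95, and with random slopes from 0.63 to 3.22.

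**A data-source term is no easy substitute.** It raises the SE from 0.034 to 0.071 with three yearly historical visits in all patients. With a single historical visit at a common time it returns the prospective-only 0.100.

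**Can values be screened as things stand?** Section 7.2.1.2 collects ocular history and previous medications. The historical data cover the section 7.2.2 assessments, which include the clinical ophthalmic examination (7.2.2.3: lens at the slit lamp, dilated fundus). Table 1, note e, adds for study visits: "Clinical ophthalmic examination will include slit lamp examination, direct and/or indirect ophthalmoscopy, and cataract grading". Where those records exist, an analyst can mark a value taken through an opacity or soon after surgery.

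**The case for a change.** The strongest case for a change is that screening decided after the rates are seen is open to choice, whereas one or two sentences in section 8.2 would settle it beforehand. In the least favourable setting the bias matters. With −3, −2, −1 in all patients and 10% affected throughout, a simulation of 300 runs with a true slope of −0.200 gave a mean of −0.149 (consistent with −0.200 + 0.051) and 72% coverage of the 95% interval. With the affected values left out, coverage was 93%. Printing the prospective rate alongside would not reliably expose such a shift, because its SE is 0.100.

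Part of this stands: the documents contain no selection rule, and a report of the combined rate should say how values were screened and how many were dropped. The rest is weaker. The 72% belongs to a long-standing, constant deficit in a tenth of patients, which nothing in the documents indicates. No patient is shown to have been in a drug study, and no offset between historical and study methods is shown; section 7.2.1.2 can be read as asking for the section 7.2.2 methods. Applying criteria 3, 4 and 7 to each historical value, eye by eye, would also be stricter than the study is with its own data. A condition arising at year 1 stays in, and section 4.2 excludes under criterion 4 only when both eyes are involved. Screening the pre-baseline side alone is therefore not neutral.

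**Conclusion.** No change to the plan follows. Section 8.2 leaves the choice of historical values to the analyst, in an analysis labelled secondary, within an observational study with no formal sample size. The main prospective rate cannot be affected.

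If 10% of patients with history had values 2 residual SD too low at every historical visit, the combined decline would be understated by about 0.02 to 0.06 residual SD per year (0.01 to 0.06 with random slopes). That is an upper-end scenario. With several historical visits and only the last one affected, the shift is near zero or slightly reversed. Both statements rest on assumed visit schedules, correlation, share and deficit. The shift scales with share times deficit, so it halves at a deficit of 1 residual SD.

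Whether to drop such values is a trade of bias against precision that depends on what the records show. The information for that judgement is collected. The differing wordings of criterion 4 in the synopsis and section 4.2 need reconciling as a matter of document consistency, but that does not alter this conclusion.
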